12.6.5 Clinical Laboratory Tests

A summary of observed values and change from baseline will be presented for all laboratory parameters with numerical measures using descriptive statistics. Shift tables displaying low-normal-high at baseline versus low-normal-high at end of study in a 3-by-3 contingency table will be provided. For selected laboratory parameters, scatter plots of baseline versus Week 56 results, will be produced by treatment group.

A laboratory value that is above or below normal range will be considered an abnormal value. For selected laboratory parameters, threshold limits of clinical concern will be defined as multiplicative factors of the normal ranges. The list of multiplicative factors for each laboratory parameter will be included in the Statistical Analysis Plan. The frequency and percentage of subjects with laboratory results above or below the normal range and threshold limits at each scheduled assessment or any time during the treatment will be summarized by treatment group.

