9.1.3 Treatment Week 4 Through Week 52 (Visits 3 Through 15)

- Obtain weight and waist circumference measurements;
- Administer PHQ-9 and C-SSRS questionnaires;
- Administer neurocognitive battery (CANTAB), Visit 6 only;
- Obtain vital signs;
- Measure height and calculate BMI;
- Record any changes in concomitant medications;
- Record any adverse events reported or observed;
- Perform urine pregnancy test;
- Collect study drug from previous visit, assess treatment compliance, and perform drug accountability; and dispense study medication and instruct the subject in the proper use of the study drug;
- Obtain blood sample for chemistry panel (Visits 3, 4, and 9 only);
- Obtain blood sample for hematology and lipids panel (Visit 9 only);
- Obtain blood sample for HbA1c (Visits 5 and 11 only);
- Provide diet (a 500-calorie/day deficit)/lifestyle modification and

- contraception/pregnancy counseling (female subjects); and
- Schedule the next study visit in 4 weeks (\pm 7 days).

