### 6.7.7 Laboratory Evaluations

A summary of observed values and change from baseline will be presented for all laboratory parameters with numerical measures using descriptive statistics. Shift tables displaying low-normal-high at baseline versus low-normal-high at end of study in a 3-by-3 contingency table will be provided. For selected laboratory parameters, scatter plots of baseline versus Week 56 results, will be produced by treatment group.

A laboratory value that is above or below normal range will be considered an abnormal value. For selected laboratory parameters, threshold limits of clinical concern will be defined as multiplicative factors of the normal ranges. The list of multiplicative factors for each laboratory parameter will be included in the Statistical Analysis Plan. The frequency and percentage of subjects with laboratory results above or below the normal range and threshold limits at each scheduled assessment or any time during the treatment will be summarized by treatment group.

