**Table 3: Clinical Laboratory Tests**

Fasting blood chemistry	Hematology	Other

 
• albumin
 
• alkaline phosphatase
 
• ALT
 
• AST
 
• GGT
 
• bicarbonate
 
• blood urea nitrogen
 
• serum calcium
 
• serum chloride
 
• serum sodium
 
• creatinine (and estimated creatinine clearance)
 
• glucose
 
• lactate dehydrogenase
 
• serum phosphorus
 
• serum potassium
 
• total and direct bilirubin
 
• total protein
 
• uric acid
 
	
 
• hemoglobin
 
• hematocrit
 
• red blood cell count
 
• red blood cell indices
 
• total white blood cell count
 
• white blood cell differential (neutrophils, lymphocytes, monocytes, eosinophils, and basophils)
 
• platelet count
 
	
 
• thyroid stimulating hormone
 

		Urinalysis
		
 
• midstream urinalysis with reflex microscopic evaluation
 
• pregnancy test (all female subjects)
 

		Urine Drug Screen
		
 
• cannabinoids
 
• amphetamines
 
• cocaine
 
• barbiturates
 
• benzodiazepine
 
• opiates
 

	Lipid panel	
	
 
• total cholesterol
 
• LDL-C
 
• HDL-C
 
• triglycerides
 
	
	Glycemic testing	Serology
	
 
• HbA1c
 
• insulin
 
• glucose
 
	
 
• HBsAg
 
• HCV
 
• HIV
 

All laboratory data will be reported in International System of Units (SI) and Conventional units. Out-of-reference-range values will be flagged as high (H) or low (L) in the listings.

For analysis purposes, values preceded by a "<" or a ">" sign (i.e. those below or above the limits of quantification) will be considered equal to the lower or upper limit of quantification, respectively.

For analysis by visit, analysis windowing as described in Section 5.1 will be utilized for each scheduled visit such that unscheduled visits will also be considered. For each laboratory analyte, the baseline value will be defined as last scheduled or unscheduled value collected prior to the first dose of treatment.

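### No planned laboratory table separates new from pre-existing abnormalities at the draws before end of study; baseline-to-worst shift tables would do so cheaply

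*Protocol*

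**What the plan says.** Protocol 12.6.5 (Clinical Laboratory Tests) and SAP 6.7.7 (Laboratory Evaluations) plan the same four outputs:

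- Descriptive statistics: "A summary of observed values and change from baseline will be presented for all laboratory parameters with numerical measures using descriptive statistics".
- Shift tables: "Shift tables displaying low-normal-high at baseline versus low-normal-high at end of study in a 3-by-3 contingency table will be provided".
- Scatter plots of baseline against Week 56, for selected parameters.
- By-arm counts and percentages of subjects with results "above or below the normal range and threshold limits at each scheduled assessment or any time during the treatment".

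SAP 6.7.7 defines laboratory baseline: "the baseline value will be defined as last scheduled or unscheduled value collected prior to the first dose of treatment". It also flags out-of-range values as high or low in the listings.

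Protocol 9.1.3 and Appendix 1 set the draws between baseline and Week 56: chemistry at Visits 3, 4 and 9 (Weeks 4, 8 and 28), hematology and lipids at Visit 9 (Week 28), and HbA1c at Visits 5 and 11 (Weeks 12 and 36). All are repeated at Week 56 or early termination.

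**The concern.** Only the shift tables and the scatter plots relate a subject's result to that subject's own starting point, and both use the end of the study. The design can separate that time point from drug exposure. Protocol 8.4.4 allows dose reduction and drug holidays, and Protocol 6.0 and 7.3 encourage subjects who stop drug to stay in the study and have Week 56 procedures. A subject who was normal at baseline, abnormal at Week 4 and normal again at the last draw counts as normal-to-normal.

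The out-of-range counts do reach the intermediate draws, but as written they put a subject who entered abnormal together with one who became abnormal on drug. Entry criteria leave room for this: Protocol 7.2 excludes AST and ALT only above 3 x ULN, triglycerides only from 400 mg/dL and fasting glucose only from 270 mg/dL.

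Safety is a primary objective. How many subjects in each arm became abnormal on drug is a basic safety question, and no planned laboratory table answers it for the intermediate draws.

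**Working it through.** The documents give no figure to reproduce, so the check is first of the text and then an illustration.

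**Text.** By baseline status and time:

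| Output | Uses own baseline status? | Covers intermediate draws? |
|---|---|---|
| Shift table | Yes | No |
| Scatter plot | Yes | No |
| Out-of-range counts | No condition stated | Yes |
| Change from baseline | Group summaries only | Not excluded |

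No laboratory table has both properties at the level of subjects' categories.

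**Illustration 1: what the end-of-study shift can miss.** Assumptions: subjects normal at baseline, a 5% chance of abnormality at each draw, and four post-baseline chemistry draws (Weeks 4, 8, 28 and 56). With independent draws, the share ever abnormal is 1 − 0.95^4 = 0.185. With correlated draws it is 1 − Pr(four equicorrelated standard normals all below 1.645). The end-of-study table shows 5%.

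| Latent correlation | Ever abnormal | Shown at end of study |
|---|---|---|
| 0 | 18.5% | 5/18.5 = 27% |
| 0.3 | 16.4% | 31% |
| 0.6 | 13.3% | 38% |
| 0.8 | 10.6% | 47% |
| 0.9 | 8.8% | 57% |

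The loss is smaller for other panels. With independent draws, HbA1c (three draws) gives 1 − 0.95^3 = 0.143 and 0.05/0.143 = 35%. Hematology and lipids (two draws) give 1 − 0.95^2 = 0.0975 and 0.05/0.0975 = 51%.

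**Illustration 2: what the any-time count mixes.** Let b be the share abnormal at baseline (assumed to persist) and q the new-onset share among the rest, assumed 10% on drug and 5% on placebo. The any-time share is b + (1 − b)q.

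| b | Drug | Placebo | Ratio | Difference | (1 − b) × 5% |
|---|---|---|---|---|---|
| 0% | 10.0% | 5.0% | 2.00 | 5.0 points | 5.0 |
| 5% | 14.5% | 9.75% | 1.49 | 4.75 points | 4.75 |
| 10% | 19.0% | 14.5% | 1.31 | 4.5 points | 4.5 |
| 20% | 28.0% | 24.0% | 1.17 | 4.0 points | 4.0 |
| 30% | 37.0% | 33.5% | 1.10 | 3.5 points | 3.5 |

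The ratio shrinks. The difference equals the true excess of new cases among all subjects in every row.

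**Chance imbalance.** That equality holds on average over randomizations. For top-dose (100) against placebo (50), the chance difference in baseline abnormality has SD √[b(1 − b)(1/50 + 1/100)], which is 3.8, 5.2 and 6.9 points at b = 5%, 10% and 20%. This is about as large as the excess itself.

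**In subjects.** For 100 on top-dose with q = 10% and b = 10%, the any-time count is 10 + 9 = 19, of whom 9 (47%) are new. If half of the 9 resolve by the last draw, the end-of-study shift shows 4.5. A baseline-to-worst shift shows all 9.

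**The case against.** The strongest reply is that most of the ground is covered already.

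- The counts are planned per scheduled draw and by arm. A reader might infer that abnormalities at Weeks 4, 8 and 28 go untabulated. The documents do not support that. Only the split into new and pre-existing is missing.
- Protocol 11.1.3 makes an abnormal result an adverse event if it is symptomatic, needs work-up or intervention, changes dosing, leads to discontinuation or is judged clinically significant. SAP 6.7.6 tabulates treatment-emergent events by arm, with an overview row for events leading to dose reduction. Dose-limiting findings therefore do appear in a table. This stands, but those tables hold only findings that meet the criteria, partly on investigator judgment. Transient changes on which no one acted are left out.
- Protocol 9.1.4 places the end-of-study visit of early withdrawals at the end of their treatment, so some changes will still be present then. This does not help for subjects who stay in the study off drug or on a reduced dose.
- Bicarbonate below the lower limit is excluded at screening, so counts of low bicarbonate are in effect new cases. The same would hold for AST and ALT above 3 x ULN if that threshold is used; the SAP lists no threshold factors. The gap concerns the other analytes and limits.
- A reader might infer that the any-time count hides the arm difference. It does not: the absolute difference is preserved on average, and only the ratio is pulled toward 1.
- The text is silent on baseline rather than explicit in ignoring it. SAP 6.1 lets table shells change denominators, and the shells are not part of these documents.

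Listings with high and low flags and review by the Data Monitoring Committee are useful, but neither gives a rate of new abnormality by arm.

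**Conclusion.** The point holds as a gap in the planned tables. Protocol and SAP agree with each other, but neither plans a laboratory table that crosses baseline status with intermediate or worst on-treatment status.

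Under the assumptions above, the end-of-study shift shows about 27% to 57% of the subjects with any abnormal chemistry draw, and the any-time count turns a true ratio of 2.0 into 1.49 to 1.10. The 5% per draw, the correlations, the baseline prevalences and the new-onset rates are all assumed, so these figures indicate direction and rough size only.

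It would go too far to say that safety signals before Week 56 would be lost. By-visit counts, change-from-baseline summaries and adverse event tables remain. This is a cheap improvement, not a flaw that undermines the safety analysis.

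**What to change.** In SAP 6.7.7, and in Protocol 12.6.5 if it is amended for other reasons:

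1. For each analyte, add two 3-by-3 shift tables: baseline to the lowest and baseline to the highest on-treatment value. State the on-treatment window, for example first to last dose. Keep the end-of-study shift.
2. Report the any-time and by-visit counts also among subjects not already outside that limit, in that direction, at baseline, and show that denominator.
3. Base the main version on scheduled draws and add a version with unscheduled draws, because retesting may differ by arm.

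The cost is SAP wording and programming, with two more shift tables per analyte and extra count columns. No visit, sample or subject is added. A worst value over several draws also raises the chance rate of abnormality in every arm: 5% per draw becomes 18.5% over four independent draws with no drug effect. The new tables must therefore be read against placebo, not as absolute rates.

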12.6.6 Vital Signs and Other Safety Evaluations

Mean blood pressures, heart rate, respiration, rate and temperature, obtained at each visit, will be summarized and plotted by treatment group. Medications, other than study medication, taken during the study will be considered as concomitant medications. They will be summarized by treatment group according to the preferred terms, using the World Health Organization (WHO) Drug Dictionary.

12.7 Interim Analysis

No interim analysis is planned.

12.8 Data Monitoring Committee

An independent Data Monitoring Committee (DMC) with multidisciplinary representation will be established to evaluate accumulating trial data on a periodic basis and to assess the ongoing safety of the study for the subjects enrolled and to be enrolled. As a result, following each data review, the DMC will make a recommendation to the sponsor regarding continuation, revision, or termination of the study. Details related to DMC responsibilities, authorities, and procedures will be documented in the DMC charter, which will be finalized by the DMC prior to the first DMC data review meeting.

13.0 TRIAL TERMINATION CRITERIA

Premature termination of this clinical trial may occur because of a regulatory authority decision, change in opinion of the institutional review board (IRB)/independent ethics committee (IEC), drug safety problems, or at the discretion of VIVUS. In addition, VIVUS retains the right to discontinue this study at any time.

If a clinical trial is prematurely terminated or discontinued, VIVUS will promptly notify the investigator. After notification, the investigator must contact all participating subjects within 2 – 3 days. As directed by VIVUS, all study materials must be collected and all CRFs completed to the greatest extent possible.

14.0 DIRECT ACCESS TO SOURCE DATA/DOCUMENTATION

Data generated by this clinical trial must be available for inspection by the FDA, by the sponsor or a designate acting on behalf of the sponsor, by applicable foreign health authorities, and by the IRB or IEC as appropriate. At a subject's request, medical information may be given to their personal physician or other appropriate medical personnel responsible for their welfare.

Subject medical information obtained during the course of this study is confidential and disclosure to third parties other than those noted above is prohibited.

15.0 QUALITY CONTROL AND QUALITY ASSURANCE

During trial conduct, VIVUS or its designee will conduct periodic monitoring visits to ensure that the protocol and Good Clinical Practice (GCP) are being followed. The monitors may review source documents to confirm that the data recorded on CRFs are accurate. The investigator and institution will allow VIVUS monitors or its agents and appropriate regulatory authorities direct access to source documents to perform this verification.

The study site and study-related documents may be subject to review by the IRB/IEC, and/or to quality assurance audits performed by VIVUS or its agents, and/or to inspection by appropriate regulatory authorities.

It is important that the investigator(s) and their relevant personnel are available during the monitoring visits and possible audits or inspections and that sufficient time is devoted to the process.

16.0 ETHICAL CONSIDERATIONS

16.1 Institutional Review Board /Independent Ethics Committee

Regulations require that an IRB/IEC oversee all investigational drug clinical trials. This board or committee, the makeup of which must conform to local and regional regulations, will approve all aspects of the trial, including the protocol, advertising and written informed consent form (ICF) to be used prior to initiation of the trial. It is the responsibility of the investigator to have prospective approval of the clinical trial protocol, protocol amendments, informed consent forms, and other relevant documents, e.g., advertisements, if applicable, from the IRB/IEC. All correspondence with the IRB/IEC should be retained in the investigator file. Copies of IRB/IEC

approvals should be forwarded to VIVUS or its designee.

Amendments to the protocol must be reviewed and approved by VIVUS and the IRB/IEC prior to implementation. The only circumstance in which an amendment may be initiated prior to IRB/IEC approval is where the change is necessary to eliminate apparent immediate hazards to the subjects. In that event, the investigator must notify the IRB/IEC and VIVUS in writing within 5 working days after the implementation.

The investigator is responsible for keeping the IRB/IEC advised of the progress of the study and of any changes made to the protocol as deemed appropriate.

16.2 Ethical Conduct of the Clinical Trial

The clinical trial will be performed in accordance with the protocol, International Conference on Harmonization Good Clinical Practice (ICH GCP) guidelines, and applicable local regulatory requirements and laws.

16.3 Subject Information and Consent/Accent

The informed consent form and any changes to the informed consent form during the course of the trial must be agreed to by VIVUS and the IRB/IEC and must be in compliance with ICH GCP, local regulatory requirements, and legal requirements.

The investigator or designee(s) must ensure that each clinical study subject is fully informed about the nature and objectives of the clinical trial and possible risks associated with participation. The investigator or designee(s) will obtain written informed consent from each subject before any trial-specific activity is performed. The informed consent form used in this clinical trial, and any changes made during the course of the trial, must be prospectively approved by both the IRB/IEC and VIVUS before use. The original signed copy of the informed consent form must be maintained by the investigator and is subject to inspection by a representative of VIVUS, their representatives, auditors, the IRB/IEC and/or regulatory agencies. A copy of the signed informed consent form will be given to the subject.

Parental consent and/or subject assent will be obtained according to IRB/IEC guidelines.

17.0 DATA HANDLING AND RECORD KEEPING

17.1 Case Report Forms/Electronic Data Record

As used in this protocol, the term CRF should be understood to refer to either a paper form or an electronic data record or both, depending on the data collection method used in this clinical trial.

A CRF is required and should be completed for each included subject. The completed original CRFs are the sole property of VIVUS and should not be made available in any form to third parties, except for authorized representatives of VIVUS or appropriate regulatory authorities, without written permission from VIVUS.

It is the investigator's responsibility to ensure completion and to review and approve all CRFs. CRFs must be signed by the investigator or by an authorized staff member. These signatures serve to attest that the information contained on the CRFs is true. At all times, the investigator

has final personal responsibility for the accuracy and authenticity of all clinical and laboratory data entered on the CRFs. Subject source documents are the physician's subject records maintained at the study site. In most cases, the source documents will be the hospital's or the physician's chart. In cases where the source documents are the hospital or the physician's chart, the information collected on the CRFs must match those charts.

In some cases, the CRF may also serve as the source document. In these cases, VIVUS and the investigator must prospectively document which items will be recorded in the source documents and for which items the CRF will stand as the source document. A CRF is required and should be completed for each randomized subject. The completed original CRFs are the sole property of VIVUS and should not be made available in any form to third parties, except for authorized representatives of VIVUS or appropriate regulatory authorities, without written permission from VIVUS.

17.2 Record Retention

To enable evaluations and/or audits from regulatory authorities or VIVUS, the investigator agrees to keep records, including the identity of all participating subjects (sufficient information to link records, e.g., CRFs and hospital records), all original signed informed consent forms, copies of all CRFs, SAE forms, source documents, and detailed records of treatment disposition. The records should be retained by the investigator according to ICH, local regulations, or as specified in the Clinical Trial Agreement, whichever is longer.

If the investigator relocates, retires, or for any reason withdraws from the study, VIVUS should be prospectively notified. The study records must be transferred to an acceptable designee, such as another investigator, another institution, or to VIVUS. The investigator must obtain VIVUS' written permission from VIVUS before disposing of any records prior to completion of the required/stipulated retention period.

18.0 PUBLICATION PLAN

Publication of study results is addressed in the Clinical Trial Agreement with each site.

All information and data, including the terms of this protocol, and all data, clinical results, and research conducted hereunder concerning VIVUS's products and operations including VIVUS patent applications, formulas, manufacturing processes, basic scientific data, and formulation information that has been supplied by VIVUS and not previously published are considered confidential by VIVUS and will remain the sole property of VIVUS. The investigator understands and agrees that said proprietary and/or confidential information disclosed to or produced by him/her there under is highly valuable to VIVUS and will be used exclusively by the Investigator in accomplishing this clinical trial and will not be used for any other purposes.

APPENDIX 1: SCHEDULE OF EVENTS

	Screening	Baseline ^a (+ 3 days)	Treatment (± 1 Week)														
			0	4	8	12	16	20	24	28	32	36	40	44	48	52	56/ET
Study Weeks→	Screen	1	2	3	4	5	6	7	8	9	10	11	12	13	14	15	16
Informed Consent/Accent	X																
Demographics and Medical History	X																
Review Inclusion/Exclusion	X	X															
Weight, Waist Circumference, Height, and BMI	X	X	X	X	X	X	X	X	X	X	X	X	X	X	X	X	
Physical Exam (include Tanner Staging)		X														X	
Concomitant Medication	X	X	X	X	X	X	X	X	X	X	X	X	X	X	X	X	
Vital Signs	X	X	X	X	X	X	X	X	X	X	X	X	X	X	X	X	
Adverse Events		X	X	X	X	X	X	X	X	X	X	X	X	X	X	X	
PHQ-9/C-SSRS	X	X	X	X	X	X	X	X	X	X	X	X	X	X	X	X	
Electrocardiogram		X														X	
DXA (selected sites only)		X														X	
Chemistry (Fasting)	X		X	X						X						X	
Hematology/Lipids	X									X						X	
TSH, HIV, HCV, HBsAg	X																
HbA1c	X					X						X				X	
Urinalysis	X															X	
Urine Drug Screen	X																
Urine Pregnancy Test	X	X	X	X	X	X	X	X	X	X	X	X	X	X	X	X	
Hand and Wrist X-ray (bone age assessment)		X														X	
OGTT ^b		X														X	
Cognitive Battery (CANTAB)	X ^c	X			X											X	
IWQOL-Kids		X														X	
Diet/Lifestyle Counseling		X	X	X	X	X	X	X	X	X	X	X	X	X	X	X	
Contraception/Pregnancy Counseling	X	X	X	X	X	X	X	X	X	X	X	X	X	X	X	X	
Randomization		X															
Dispense Study Drug		X	X	X	X	X	X	X	X	X	X	X	X	X	X	X	
Drug Accountability			X	X	X	X	X	X	X	X	X	X	X	X	X	X	
Schedule Next Visit	X	X	X	X	X	X	X	X	X	X	X	X	X	X	X	X	

^a Baseline can occur up to 4 weeks from Screening.^b Blood sample at 2 hours post glucose load^c Familiarization session only

